# **PROTOCOL SUMMARY**

ITEM	DESCRIPTION		
Title	GYROS: Gyrate Atrophy Ocular and Systemic Study		
Précis	GYROS: Gyrate Atrophy Ocular and Systemic Study Gyrate atrophy (GA) is a rare inherited chorioretinal degeneration that is associated with hyperornithinemia, an inborn error of metabolism caused by autosomal recessive mutations in the ornithine aminotransferase ( OAT ) gene. GA is characterized by childhood-onset nyctalopia and sharply demarcated areas of chorioretinal atrophy that initially involve the midperipheral fundus. The atrophic areas typically coalesce and enlarge towards the posterior pole in the second and third decades of life, leading to severe visual field constriction and vision loss if left untreated. The current standard care treatment of GA is an arginine restricted diet that is implemented in practice using dietary protein restriction with essential amino acid supplementation. However, dietary treatment is highly burdensome on patients and negatively impacts quality of life such that only about ~20% of patients can comply. Strict adherence to dietary protein restriction (particularly through adolescence), essential amino acid supplementation, and nutritional management of body weight especially during intercurrent illness and pregnancy are among the challenges of treatment. Periods of suboptimal dietary control led to plasma ornithine elevation and progressive chorioretinal degeneration. To facilitate a future interventional gene therapy clinical trial, there is a need to evaluate natural history of and the relationship between potential clinical trial outcome measures.		

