#### 217 **1.5.3 Risk Assessment**

- The known potential risks above, except for venipuncture, fingerstick collection and skin biopsy, are standard-of-care procedures that do not pose additional risks to participate in the study.
- The venipuncture is needed to collect plasma samples to monitor the ornithine levels in relation to progression of Gyrate Atrophy.
- A fingerstick blood spot collection is needed to obtain a blood spot sample. This will
   determine if this procedure is comparable to the plasma sample collection in evaluating
   the ornithine levels over time.
- A skin biopsy is an incisional procedure of the skin. The potential complications include 225 localized bleeding, scarring, bruising, pain, redness, swelling, and damage to nerves and 226 blood vessels. These complications are rare, and when they occur, are mild and self-227 limiting. This procedure will be used to collect the participant's cells, which are 228 fibroblasts. These cells will be used to measure the activity of the participant's OAT 229 enzyme and the response to vitamin B6. The research goal is to understand the impact of 230 OAT mutations on plasma ornithine levels and retinal degeneration. The skin biopsy is 231 necessary to quantify OAT enzyme activity in each participant as it is not possible to 232 derive this information from the blood sample, thus providing direct confirmation on the 233 pathogenicity and functional severity of the mutation in each subject. This information 234 will inform the analysis of the plasma ornithine and retinal degeneration outcome 235 measures for the duration of this trial and will complement the development of dietary 236 guidelines for treatment trials in slowing the progression of Gyrate Atrophy. The cells 237 can be stored frozen indefinitely with participant consent. These cells can be re-cultured 238 to perform additional studies as needed to provide a better understanding of Gyrate 239 Atrophy. 240

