1188	mitigate the impact of missing data, specifically, mixed effects
1189	regression models and multiple imputation for the outcome values for
1190	all missing time points.
1191	
1192	(b) Characterize the natural history of ornithine levels associated with disease-
1193	causing OAT variants in the presence of standard care dietary treatment
1194	regimens over four (4) years.
1195	
1196	i. Longitudinal annual measures of ornithine will be explored by
1197	graphing the values for everyone ("spaghetti" plots) and analyzed to
1198	detect any linear trend in time with mixed effects models.
1190	detect any mical field in time with mixed effects models.
1200	(c) Determine within-patient variability of ornithine levels associated with
1200	disease-causing OAT variants in the presence of standard care dietary
1201	treatment regimens over four (4) years.
1202	
1203	i. The within-person standard deviation of ornithine levels will be
1204	estimated for the group of patients using a mixed effects model.
1205	Models will be based on levels from blood dot tests and from plasma
1206	testing over the four (4) years to determined long -term variability and
1207	on levels from blood dot tests over periods of six (6) months and of
1208	twelve (12) months to determine short-term variability. The coefficient
1209	of repeatability will be calculated to estimate the difference from
1210	baseline that would need to be exceeded to indicate that a treatment
1211	was causing an effect beyond random variability.
1212	2. Metabolic, Structure, and Function Relationships
1213	(a) Evaluate cross-sectional associations at baseline and each annual visit with
1214	scatterplots and Spearman correlation coefficients. Evaluate the association of
1215	changes in each outcome measure with changes the other outcome measures
1216	at each visit with scatter plots and Spearman correlation coefficients. Use
1217	mixed effects regression models to evaluate the association of change in each
1218	outcome measure with changes in each of the other outcome measures. With
1219	so many outcomes and only forty (40) patients, results will be interpreted
1220	cautiously because of both low powers to detect clinically meaningful
1221	associations and elevated Type I error rates due to multiple comparisons.
1222	3. Identify Rapid Progressors
1223	(a) The distribution of each outcome in terms of both absolute change and percent
1224	change from baseline to four (4) years will be summarized (including

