1225	tabulating categorically, as well as means, standard deviations, medians,
1226	quartiles), stratified by categorical levels of each potential risk factor of
1227	interest (listed below). Potential risk factors to evaluate include phenotypic
1228	factors including the baseline level of each of the structural and functional
	-

1229	measures and ornithine level, genotype, and adherence to the arginine-
1230	restricted diet as noted below. Univariable regression models of each outcome
1231	measure will be fit for each of the potential risk factors. With so many
1232	potential risk factors and outcomes and only forty (40) patients, results will be
1233	interpreted cautiously because of both low powers to detect clinically
1234	meaningful differences and elevated Type I error rates due to multiple
1235	comparisons.
1236	
1237	i. Phenotypic:
1238	
 
Age of onset of initial vision symptoms
 

1239	
 
Gender
 

1240	Race/ethnicity
1241	
 
Body weight/BMI
 

1242	
 
Lens Status (phakic/pseudophakic/aphakic) and area of
 

1243	subcapsular cataract on red reflex photos
1244	
 
Baseline foveal avascular zone (FAZ) area and macular vessel
 

1245	density on OCTA
1246	
 
Baseline visual acuity
 

1247	
 
Baseline low luminance visual acuity
 

1248	
 
Baseline area of preserved retina on fundus autofluorescence
 

1249	and color photos
1250	
 
Baseline full Hill of Vision (HOV) on static perimetry
 

1251	
 
Baseline mean sensitivity on static perimetry
 

1252	
 
Baseline mean retinal sensitivity on microperimetry
 

1253	
 
Baseline full-field stimulus (FST) levels
 

1254	
 
Baseline ERG amplitude and timing
 

1255	
 
Baseline ellipsoid zone (EZ) area on OCT
 

1256	
 
Baseline ornithine level
 

1257	
1258	ii. Genotypic
1259	
 
Characterizations of the OAT variants
 

1260	
1261	iii. Environmental Factors
1262	
 
Adherence to arginine-restricted diet
 

1263	
 
Smoking
 

1264	

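### Section 8.3.1 relates progression to baseline ornithine and to change in ornithine, but not to the ornithine level each participant has over follow-up

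*Protocol*

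**What the plan says.** Objective 2b in the Protocol Summary is to explore how plasma ornithine levels relate to structural and functional outcomes. Section 1.5.3 gives the reason for venipuncture: the samples are needed "to monitor the ornithine levels in relation to progression of Gyrate Atrophy". The collection schedule provides one plasma draw at screening, two at baseline and one at each of four annual visits, plus blood spots every four months.

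Section 8.3.1 uses ornithine as follows:

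- **Items 1(b) and 1(c):** the time trend of ornithine and its within-person variability. No retinal outcome is involved.
- **Item 2:** Spearman correlations between levels at the same visit; Spearman correlations of "changes in each outcome measure with changes the other outcome measures"; and "mixed effects regression models to evaluate the association of change in each" outcome with changes in the others.
- **Item 3:** univariable regressions of each outcome on single risk factors, among them "Baseline ornithine level" and "Adherence to arginine-restricted diet".

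The protocol also expects ornithine to move. The Précis says "Periods of suboptimal dietary control led to plasma ornithine elevation and progressive chorioretinal degeneration" and that "only about ~20% of patients can comply" with dietary treatment. Section 1.2.1 reports that few of more than 25 patients who started the diet kept ornithine reduced beyond five years. Section 4.3 has food-record rules for participants who start or stop the diet during the study.

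**The concern.** The disease rationale is about exposure: high ornithine over time goes with faster retinal loss. A participant whose ornithine is constantly high and who steadily loses retina has an ornithine change near zero, so correlating change with change misses the link in that participant. The same-visit correlations compare level with level, not level with rate. Baseline ornithine does address rate, but it describes exposure only while the level stays where it began. Item 3 is univariable, so baseline level and later change are not combined.

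Two things are at stake. For participants who change diet, the best available exposure measure goes unused although the samples are taken. And a null change-on-change result under objective 2b could be read as showing that ornithine level does not matter, in a study meant to inform a treatment trial.

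**Working it through.** **1. The protocol's own figures.** Section 8.2.4 gives a 95% CI of (0.24, 0.69) for r = 0.5 at an effective n of 44. Check: atanh(0.5) = 0.549; 1.96/√41 = 0.306; tanh(0.549 ± 0.306) = 0.24 and 0.69. The half width also reproduces: 1.96 × 20/√44 = 5.9%, stated as 6%. Neither is in dispute.

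**2. Why the exposure measure matters.** Take N = 40 (section 8.3.1), two-sided 5%, and an assumed correlation of 0.5 between true mean ornithine over four years and 4-year change. If the predictor used correlates λ with that true mean, approximate power is Φ(atanh(0.5λ)·√37 − 1.96):

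- λ = 1: 0.549 × 6.083 − 1.96 = 1.38, power 92%
- λ = 0.96: 0.523 × 6.083 − 1.96 = 1.22, power 89%
- λ = 0.9: 0.485 × 6.083 − 1.96 = 0.99, power 84%
- λ = 0.77: 0.406 × 6.083 − 1.96 = 0.51, power 70%
- λ = 0 (change in ornithine when levels are stable): rejection rate 5%, which is alpha

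**3. Simulation with diet switching.** From the protocol: N = 40, 4-year SD 20% (section 8.2.4), two baseline draws, about 20% able to comply. Assumed: correlation 0.5; off-diet median 700 µmol/L with log-SD 0.25; on-diet level 35% of that; within-person CV 20%; 20% or 40% on diet at baseline; switch times uniform over four years; and every switching rate. Power in % (20% / 40% on diet), one value per participant, 4,000 runs:

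| Scenario | Baseline level (two draws) | Mean plasma level | Change-on-change (Spearman) |
|---|---|---|---|
| Stable | 88.5 / 89.9 | 91.1 / 91.7 | 5.9 / 5.4 |
| Half of dieters stop | 82.7 / 82.0 | 89.7 / 90.8 | 6.7 / 6.6 |
| Half stop, a quarter of the others start | 67.2 / 70.5 | 90.7 / 91.2 | 6.0 / 5.2 |

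The mixed-model form of change-on-change gave 4.4–7.2%. With milder switching, baseline level has 86% power if a quarter of dieters stop, and 81–83% if 10% of the others also start, against 90–91% for mean plasma level. If three quarters of dieters stop, change-on-change reaches 8.8–9.2%. A perfectly recorded share of time on diet, the best case for the adherence proxy, has 57–68% with 20% on diet and 74–80% with 40%.

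At an assumed correlation of 0.3 with 40% on diet, baseline level has 45, 37 and 30% across the three table scenarios, against 47, 46 and 45% for mean plasma level.

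**4. Simulation with drift.** Here each participant's ornithine drifts linearly. The between-person share of variance (ICC) is 0.5 to 0.9, and drift SD over four years is in units of the SD of a single measurement. Again N = 40 and correlation 0.5, with Spearman tests and 20,000 runs:

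| Drift SD | Change-on-change | Baseline level | Mean of four follow-up levels |
|---|---|---|---|
| 0 | 5% | 71–87% | 80–87% |
| 0.5 | 8–9% | 65–84% | 81–87% |
| 1.0 | 24–25% | 51–76% | 83–87% |

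So change-on-change does pick up part of the relationship when levels drift, but far less than the follow-up mean does. The 9-point gap with no drift occurs only at ICC 0.5, where single measurements are noisy.

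**The case against.** The strongest reply is that this is SAP detail. Section 8.1 calls the chapter a synopsis and framework, and item 3 says that the risk factors include those listed, so nothing excludes a mean-level predictor. Objective 2b does not mention rate, and the same-visit correlations answer it as worded. The link to progression comes from a sentence in the risk section, not from an objective. Much of this stands, and it is why the point is minor. What remains is that the protocol names its longitudinal methods and its ornithine predictor, and an SAP that follows them would leave the purpose in section 1.5.3 only partly served.

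The size is also assumption-driven. The protocol gives no switching rate, correlation or ornithine variability, and section 4.3 only sets food-record logistics. That stands in full.

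A reader might infer three stronger claims that the documents do not support:

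- *Progression is never related to follow-up ornithine.* It is, as change scores; what is missing is the level.
- *Change-on-change always has power near alpha.* That holds for stable levels and most switching patterns, but not under marked drift.
- *A running-mean-by-time model is required.* In simulation it reached 96–98% under heavy switching, but the data were generated from cumulative exposure, so that partly reflects fitting the generating model. With stable levels and 20% on diet, its plasma version was 6 points below the baseline regression (82.6 against 88.5%). A plain mean level had no such loss.

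Items 2 and 3 already caution about low power and multiplicity. They do not say that change-on-change answers a different question from level.

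**Conclusion.** The point holds as a cheap improvement, not as a flaw that defeats an objective (severity: could change). No analysis stated in section 8.3.1 uses a participant's ornithine level over follow-up to predict progression, although section 1.5.3 presents the plasma draws as serving that purpose. With 40 participants and an assumed correlation of 0.5, relying on baseline level costs about 1–3 points of power if ornithine is stable with a within-person CV of 20%, about 5–10 with mild diet switching, and a little over 20 with heavy switching. Change-on-change cannot fill the gap: it has about 4–9% power with stable levels or switching, and about 10–25% with drift (8–9% at the milder drift shown). If ornithine proves stable in this cohort, the existing baseline regression is nearly enough.

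**What to change.** In item 2 or item 3 of section 8.3.1, add the participant's mean plasma ornithine over baseline and follow-up visits as a predictor of 4-year change in each structural and functional outcome, or of slope through its interaction with time in the mixed model. Keep the baseline regression and the existing correlations. Add one sentence saying that a null change-on-change result is not evidence against a relationship with ornithine level.

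A time-updated running-mean-by-time model is an optional sensitivity analysis. So is a blood-spot version, fitted separately because the study has yet to "determine if this procedure is comparable to the plasma sample collection in evaluating" ornithine over time.

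The cost is wording only, since every sample is already scheduled. The downsides are one more exploratory predictor per outcome, under the multiplicity caution already in items 2 and 3, and an association that stays observational, because participants may change diet in response to vision loss.

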Impact	
 
disease-causing OAT variants.
 
The expected impact of the OAT gene natural history study is to inform a future interventional clinical trial design and implementation, including the following: 
 
Determine within-patient variability of ornithine levels.
 
Develop quantitative measures of progression of the area of preserved retina and establish its reproducibility, sensitivity to change, and relationship with other measures.
 
Establish rates of progression of retinal degeneration on all functional, structural, and patient-reported outcome measures, and determine which measures are most sensitive to change.
 
Determine primary time points and duration for a planned future treatment trial.
 
Use variability and inter-eye correlation of outcomes for trial sample size calculations.
 
Identify candidates for the future trial, including eligibility criteria based on risk factors and cut points for severity of disease most likely to benefit from treatment.
 
 
 
			
Study Design Number of Sites	Multicenter, longitudinal, pro assigned to one (1) of three (2 kinetic visual fields (VF). Approximately 12			
	Structural Outcomes:	1		
	Key Assessments	Test	Equipment	Reading Center
Outcomes	Primary: Quantitative measures of progression of the area of preserved retina and of the area of lesions in standardized regions*	Fundus autofluorescence (FAF)	Optos	Yes
	Primary: Use with FAF for assessments noted above	Ultra-Widefield Color Photography	Optos	Yes
	Ellipsoid zone (EZ) area	Spectral domain optical coherence tomography (SD-OCT)	Heidelberg Spectralis	Yes
	Presence and type of cataract (posterior subcapsular and cortical cataract) **	Red reflex photography	Digital camera capable of capturing external eye photos Megapixels of >=3MP Magnification of 30-40 degrees Digital camera export in PNG, TIF, DICOM or BMP	Yes

ITEM	DESCRIPTION			
	Foveal avascular zone (FAZ) area and macular vessel density	OCTA Ancillary test at subse sites	list	Yes
	*Other approaches to grading m **Ocular exam by investigator v cataract. Functional Outcomes:			uclear sclerosis
	Key Assessments	Test	Equipment	Reading Center
	Visual field sensitivity measured with quantitative topographic analysis (Hill of Vision)	Static Perimetry	Octopus 900 Pro	Yes

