## 8.2.2 Sample Size Considerations for Comparing Percent Change from Baseline to four (4) Years within Subgroups of Interest – All Outcomes

1061 Another objective for this natural history study will be to explore the association of risk factors 1062 with progression of various functional outcome variables (objective 3). **Figure 6.1** considers 1063 various expected SDs of the distribution of percent change from baseline to four (4) years per

eye and evaluates the power to detect varying differences in average percent change from

- baseline to four (4) years, comparing subgroups of various equally distributed sizes. If subgroups
- are not equally sized the smallest detectable difference (with the same power) will be larger.
- 1067 Testing will be performed with a Type I ( $\alpha$ ) error rate of 0.05.
- Note: *within* subgroup point estimates and Cis will also be important. Table 6.1 above can be
   applied to potential subgroup sample sizes as well to consider the precision that would be
   observed.

[figure not shown]

Figure 6.1. Power to conclude there is a difference given varying true difference values, population standard
 deviation, and sample size.

1073 For the graphs is Figure 6.1, the y-axis if for the power to conclude that there is a difference

1074 when the true difference in mean percent change is the x-axis value. Each of the four graphs is

1075 for a different total sample size with the number of eyes in each of the two subgroups being

1076 approximately fifty percent (50%). Forty (40) participants from Vision Cohorts 1 and 2 will be 1077 followed.

For example, with an effective sample size of twenty-two (22) and an effective sample size of eleven (11) in each subgroup, to have power of 80% or more, the true difference needs to be

approximately 1.25 SDs (a mean difference of 25% if the SD of the percent change over four (4)

- years 20%). If the effective sample size is thirty-three (33), the true difference needs to be
- approximately 1.0 SD (a mean difference 20% if the SD of the percent change over four (4)
- years is 20%). If the effective sample size is forty-four (44), the true difference needs to be
- approximately 0.86 SDs (a mean difference 17% if the SD of the percent change over four (4)
- 1085 years is 20%). Such mean differences are considered large.

1086 **8.2.3 Sample Size Considerations for Precision of the Estimate of the Correlation** 

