#### Data to consider for evaluating sample size: 1109

- Valproic Acid Protocol (VPA) Data (phase II multiple sites, randomized, placebo-1110 1111 controlled trial of oral valproic acid for ADRP) [Placebo group N=44; dataset can be accessed at https://public.jaeb.org/ffb/stdy] 1112
  - Percent Change from Baseline to 1 year, Mean (SD):
- 1114

1113

1118

1120

- -0.3% (16%) OD -4.9% (17%) OS
- 1115 1116 **Assumptions made:**
- Expect average annual decline due to *OAT* will be 5% per year or 20% by four (4) years. 1117
- True SD of percent change at four (4) years is like VPA 1-year SD of approximately 20%. 1119

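### The rapid-progressor analysis regresses each outcome's four-year change on that outcome's own measured baseline, which is biased, and no single change scale makes the result neutral

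*Protocol*

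**What the plan says.** Protocol Section 8.3.1, item 3(a), begins: "The distribution of each outcome in terms of both absolute change and percent" change from baseline to four years will be summarised, stratified by levels of each risk factor. The risk factors take in "factors including the baseline level of each of the structural and functional" measures. The list that follows names, among others, "Baseline area of preserved retina on fundus autofluorescence" and color photos, ellipsoid zone area, static perimetry and microperimetry. Baseline lesion area is not named, but the general wording covers it.

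The regressions are described as "Univariable regression models of each outcome" measure, one risk factor at a time. The change scale for these regressions is not given. The stated caution is about low power and multiple comparisons.

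Three other places bear on the point:

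- The primary structural outcome in the Protocol Summary is "Quantitative measures of progression of the area of preserved retina and of the area of lesions in standardized regions".
- Section 8.2.2 works the power for objective 3 on "various expected SDs of the distribution of percent change from baseline to four (4) years per" eye, that is, on the percent scale only.
- The Impact list in the Protocol Summary expects the study to yield "eligibility criteria based on risk factors and cut points for severity of disease most likely to benefit from treatment".

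**The concern.** Two separate problems arise when an outcome's change is related to its own baseline.

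1. **Regression to the mean.** An eye whose baseline is measured too high will, on average, appear to lose more. This affects absolute and percent change alike.
2. **A shared denominator.** Percent change divides by the risk factor itself. The same loss is a small percentage of a large area and a large percentage of a small one. If lesion area grows as preserved area shrinks, the two percent changes react to stage in opposite ways.

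Section 1.1.1 describes lesions that enlarge over decades, and the Vision Cohorts in Section 2.1.1.1 span a wide range of severity, so baseline areas will vary a great deal. At stake is the severity information passed to the future trial. A gradient produced by measurement error or by the choice of scale could be read as a real difference in progression by stage and turned into an eligibility cut point. The planned caution about power and multiplicity does not address a systematic bias.

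**Working it through.** **The plan's own figures (Sections 8.2.1, 8.2.2 and 8.2.4).** Effective N = 40 × 2/(1 + 0.8) = 44.4. Half-width = 1.96 × 20/√44 = 5.9%, stated as 6%. Power for 22 per subgroup at 0.86 SD (17%) is 0.81 by the normal formula and 0.80 by the t-test, stated as about 80%. These reproduce.

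**Step 1: baseline error.** Take measured baseline b = T + e0 and follow-up f = T + d + e1, with T of variance 1 and true change d independent of T. Reliability ρ gives error variance v = (1 − ρ)/ρ. Then

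corr(b, f − b) = −v / √[(1 + v)(σd² + 2v)].

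The true association is zero. Reliability and σd are assumptions, because the protocol gives neither. The rejection rates are simulated with n = 40 and two-sided 0.05 (|r| > 0.312), and carry simulation error of about one percentage point.

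| ρ | v | σd | expected r | null rejected |
|---|---|---|---|---|
| 0.95 | 0.053 | 0.3 | −0.12 | about 11% |
| 0.90 | 0.111 | 0.3 | −0.19 | about 22% |
| 0.80 | 0.250 | 0.3 | −0.29 | about 46% |
| 0.95 | 0.053 | 1.0 | −0.05 | about 5% |
| 0.80 | 0.250 | 1.0 | −0.18 | about 19% |

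At reliability 0.99 and σd 0.3 the rate is about 6%, so with a very precise measure this part almost vanishes.

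**Step 2: denominator, worked by hand.** Assume a region of 100 units in which preserved area P and lesion area sum to 100. Let every eye lose 10 units, which is the protocol's expected decline ("will be 5% per year or 20% by four (4) years") at P = 50.

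| P | preserved | lesion |
|---|---|---|
| 80 | −10/80 = −12.5% | +10/20 = +50% |
| 50 | −20% | +20% |
| 20 | −10/20 = −50% | +10/80 = +12.5% |

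Preserved area marks the late eye as fast, lesion area marks the early eye as fast, and absolute change marks neither.

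**Step 3: size under constant absolute loss.** With P from 15 to 85, loss mean 8 points and n = 40, both percent measures correlate with their own baseline at |r| about 0.71 and reject in over 99% of runs when the loss SD is 3 points. At loss SD 8 the rate is about 69%. With P from 20 to 80, mean loss 10 and a spread of loss of about half its mean, percent preserved change averages −34% for P 20–40 and −14% for P 60–80. That 20-point gap exceeds the 17% difference the study is powered to detect.

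**Step 4: other loss laws.** P from 20 to 80, n = 40, measurement SD 2 units (assumed). Entries are rejection rates for regression on own baseline.

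| Loss | absolute | % preserved | % lesion |
|---|---|---|---|
| constant | 6% | 92% | 97% |
| proportional to P | 96% | 7% | 100% |
| proportional to lesion area | 87% | 100% | 9% |
| proportional to √(lesion area) | 33% | 99.8% | 62% |

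Under every law tried, at least one percent measure depends on stage. Absolute change is close to neutral only under the first.

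**The case against.** Several points on the other side have force.

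- Absolute change is planned next to percent change, so a reader comparing them would see part of the artefact. This stands. It would be wrong to infer that the choice of denominator alone answers objective 3; genotype, diet and the other risk factors are also not subject to this own-baseline coupling.
- The protocol does not say that the regressions use percent change. This also stands, and Section 8.1 calls the chapter a framework for the final analysis plan, so the scale may be settled there. The pairing of change with its own baseline is nevertheless stated in the protocol, and step 1 applies on either scale.
- A reader might infer that percent change depends on stage by construction, or that the two areas must always disagree. The documents do not support this. They state no loss law, and Section 8.2.4 expresses the expected decline as a percentage. If loss is proportional to preserved area, percent preserved change is free of stage. Nor does the protocol say that preserved and lesion area fill a fixed region.
- A reader might conclude that absolute area change should therefore be the deciding scale. The second and third rows of step 4 show that it can depend on stage just as strongly.
- The objective is exploratory and its results are to be read cautiously. True, but that caution names only power and multiplicity, and the Impact list looks to the study for severity cut points.

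**Conclusion.** The concern holds in this form: testing each outcome's four-year change against its own measured baseline is biased, and for the area measures the answer also depends on the scale, with no scale neutral in general.

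The error part produces a false association in about 11% to 46% of analyses at reliability 0.95 to 0.80 if true change is small relative to the baseline spread (SD 0.3), and in about 5% to 19% if it is as large as that spread (SD 1.0). The denominator part ranges from absent to near-certain according to the loss law and the spread of loss. Its opposite-direction form rests on preserved and lesion area being complements.

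These magnitudes rest on assumed reliabilities, loss laws and spreads, with n = 40 independent units. They show what the planned analysis can do, and do not predict what GYROS will find.

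**What to change.** In Section 8.3.1, item 3, add a rule for the case where the risk factor is the outcome's own baseline level, or the complementary area:

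1. Do not test it by regressing change or percent change on that measured baseline.
2. Estimate dependence on severity from the covariance of random intercept and random slope in the item 1(a)i mixed model, with time zero at baseline. That model already uses baseline and all annual visits; the text should say that it includes a random slope. Alternatively, use a stage marker from a different test, for example Vision Cohort for the imaging outcomes. Vision Cohort is built partly on the screening visual acuity score, so it is not a separate marker for acuity.
3. Report percent change by own baseline as description only.
4. Before any severity gradient or cut point is carried to the future trial, show whether it holds on the absolute, square-root-area and percent scales. A separate stage marker removes the shared error but not the dependence on scale, so this step is needed in either case.
5. Extend the caution in item 3 to regression to the mean and choice of scale.

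The cost is wording and some extra analysis, with no new data or visits. The main downside is that an intercept-slope covariance will be imprecise with about 40 participants, so its confidence interval should be shown.
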